13.2.5. Untoward medical events unrelated to the trial – not reportable

It is anticipated that there will be minimal additional risks associated with the interventions in this trial. Participants treated may have co-morbidities and in recognition of this, untoward medical events will only be reported if they are classified as related to trial procedures (including the intervention and related procedures or trial-specific procedures such as consent and questionnaire completion).

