6.2. SECONDARY OBJECTIVES

To examine and report:

- 1) Patient reported outcomes and quality of life within 24 months after surgery
- 2) Objective assessment of knee function
- 3) Rates of complications, including infection
- 4) The need for further intervention within 24 months after surgery
- 5) KJD's potential as a cartilage regenerative therapy
- 6) Estimate of short and long term cost-effectiveness
- 7) Implementation processes and intervention fidelity
- 8) Participant experiences of the trial/interventions and possible facilitators or barriers to wider implementation

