7. DESIGN

7.1. TRIAL DESIGN SUMMARY

KARDS is a multi-centre, pragmatic, open-label, two-arm individually randomised controlled non-inferiority trial. The trial has a non-inferiority design based on PPI feedback indicating a strong preference to retain the knee with KJD over KR providing there is no worse knee pain.

A total of 344 participants will be randomised on a 1:1 basis between KJD and KR, stratified by surgical delivery unit and osteoarthritis severity (Section 14).

A hybrid expertise design will be used to account for surgeon expertise in the surgical procedures and potential lack of individual equipoise (Section 8.2).

The trial has an embedded 12-month internal pilot phase (Section 7.2) and process evaluation (Section 16) with selected clinicians, participants and non-recruited patients to evaluate feasibility of recruitment and address any barriers to recruitment. The qualitative process evaluation will assess clinician experience and patient acceptability during the pilot phase and throughout the main trial.

All participants will be followed for 24 months post-surgery (Section 12). The trial will not be blinded to participants, medical staff, or clinical trial staff.

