13.1. GENERAL DEFINITIONS

A **complication** is defined as an untoward medical event in a participant which has a causal relationship with the trial. This includes the trial intervention (KR or KJD surgery) and any subsequent treatment relating to the trial intervention (such as treatment of complications caused by the trial intervention and any trial-specific interventions e.g. the consent process and completion of questionnaires).

An untoward medical event can include:

- any unintentional unfavourable clinical sign or symptom;
- any new illness or disease of the deterioration of an existing condition;
- any clinically relevant deterioration in any clinical tests.

A **serious complication** (SC) is defined as a complication which meets at least one of the following criteria:

- results in death;
- is life-threatening¹;
- requires hospitalisation or prolongation of existing hospitalisation;
- results in persistent or significant disability;
- consists of a congenital anomaly or birth defect;
- is otherwise considered medically significant by the Investigator.

¹ Life-threatening refers to an event in which the participant was at risk of death at the time of the event, NOT an event which hypothetically may have caused death had it been more severe.

An **Unexpected Serious Complication** (USC) is a serious complication that is **related** and **unexpected** and will require expedited reporting to enable reporting to the main Research Ethics Committee (REC) and Sponsor. KARDS protocol $v1.0_{-}190927$

The Health Research Authority (HRA) defines the terms '**related'** and '**unexpected'** as:

- '**Related':** that is, it resulted from the administration of any of the research procedures. All complications are by definition related to the trial procedures (untoward medical events which are unrelated to the trial procedures are not being collected in this trial).
- 'Unexpected': that is, the type of event that in the opinion of the investigator is not considered expected. Examples of expected complications are provided in Section 13.2.2; note this is not an exhaustive list.

Medical and scientific judgement must be exercised in deciding whether an event is serious (see protocol Section 13.3 for Responsibilities). These characteristics / consequences must be considered at the time of the event and do not refer to an event which hypothetically may have caused one of the above.

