13.3. SAFETY REPORTING RESPONSIBILITIES

Principal Investigator (PI) (i.e. lead trial clinician at each recruiting research site or appropriate clinical individual identified in the APL)

1. Checking for complications during admission and follow-up, including using medical judgement in assigning:

- Causality, i.e. whether an untoward medical event is related (i.e. a complication which therefore needs to be reported) or unrelated (i.e. not a complication and therefore does not need to be reported)
- Seriousness
- Expectedness

3. To ensure all SCs and USCs up to 24 months are recorded and initially reported to the CTRU within 24 hours of the research site team becoming aware and to provide further follow-up information as soon as available.

4. To report SCs and USCs to the CTRU in-line with the protocol.

5. To report USCs to local committees in line with local arrangements.

Chief Investigator (CI) (or nominated individual in CI's absence)

1. Assign relatedness and expected nature of reported complications/untoward medical events where it has not been possible to obtain local assessment.

2. Undertake review of SCs and USCs. In the event of disagreement between local assessment and the CI, local assessment may be upgraded or downgraded by the CI prior to reporting to the main REC.

Clinical Trials Research Unit (CTRU)

1. Expedited reporting of USCs occurring within 24 months post-surgery to the REC and Sponsor according to HRA, CTRU SOPs and Sponsor timelines.

2. Preparing annual safety reports to the REC and periodic safety reports to TSC and DMEC as appropriate.

3. Notifying Investigators of SCs and USCs which compromise participant safety.

Trial Steering Committee (TSC)

In accordance with the Trial Terms of Reference for the TSC, periodically reviewing safety data and liaising with the DMEC regarding safety issues. See Section 21.2.2 for further detail about the responsibility of the TSC.

Data Monitoring & Ethics Committee (DMEC)

In accordance with the Trial Terms of Reference for the DMEC, periodically reviewing unblinded safety data to determine patterns and trends of events, or to identify safety issues, which would not be apparent on an individual case basis. See Section 21.2.3 for further detail about the responsibility of the DMEC.

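### Apart from deaths and unplanned surgery on the affected knee, complications are recorded only if unblinded site staff judge them related, so attribution that differs by arm could bias the comparison and could not be assessed from the trial data

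*Protocol*

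**What the plan says.** Section 13.1 defines a complication as "an untoward medical event in a participant which has a causal relationship with the trial" and adds that "untoward medical events which are unrelated to the trial procedures are not being collected in this trial". Section 13.2.5 repeats the rule: "untoward medical events will only be reported if they are classified as related to trial procedures". Under Section 13.3 the local principal investigator or delegate decides causality, and an event judged unrelated is "not a complication and therefore does not need to be reported".

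Section 7.1 states: "The trial will not be blinded to participants, medical staff, or clinical trial staff". Section 6.2 makes "Rates of complications, including infection" a secondary objective, and Section 14.1 reports complications as numbers of events and of patients with events.

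Two kinds of event are collected without a causality condition: all deaths from randomisation to 24 months (Section 12.3.3), and any unplanned surgery on the affected knee, including primary or revision replacement (Sections 11.2 and 12.2).

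**The concern.** Entry into a secondary outcome depends on a judgement about the very exposure being compared, made by people who know which arm the patient is in. The arms look different to the assessor. KJD is new to most UK sites and brings an external frame, pin sites and a second anaesthetic for frame removal, while KR is routine. A site might attribute a pneumonia or a stroke more readily to the unfamiliar procedure, or less readily if it favours that procedure. The direction cannot be known in advance.

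One strength of a randomised safety comparison is that it can show an excess of events without anyone deciding the cause of each case. That strength is given up for events that pass through this filter. If KJD meets the pain margin, its complication profile against KR will be read closely, and part of that profile would rest on attributions whose consistency between arms cannot be examined.

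**Working it through.** **1. Does any later step restore the rejected events?** Four candidates were checked against the text.

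- *Chief investigator review (Section 13.3).* It covers serious and unexpected serious complications, where "local assessment may be upgraded or downgraded by the CI prior to reporting to the main REC". It works on events already reported. The chief investigator assigns relatedness only where no local assessment could be obtained.
- *DMEC (Sections 13.3 and 20.2.3).* It sees data by arm, but its complication data have passed the same filter.
- *The expected-complications list (Section 13.2.2).* It names myocardial infarction, pneumonia, stroke and others, but introduces them as complications related to a research procedure. The filter still applies.
- *Blinded assessment.* The only blinded central review described is of the joint-space radiographs (Section 11.2). None is described for causality.

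**2. What is exposed?** Deaths, unplanned surgery on the affected knee, and hence joint survival are not filtered. Intra-operative events and failure of the frame or pins are related on their face. Surgical site infection is still subject to the filter, but its CDC classification and recorded antibiotic use leave less discretion. What remains most open to judgement over 24 months is systemic and thrombo-embolic events and fractures.

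**3. How does the bias work?** The protocol gives no complication rates or attribution shares, so there is no figure of its own to reproduce. The one input from the documents is 172 patients per arm (Section 14.2). All rates and shares below are assumptions.

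Recorded rate = true rate × share attributed. With equal true rates *p* and shares *a* and *b*, the recorded rate ratio is (*p* × *a*) / (*p* × *b*) = *a* / *b*, whatever *p* is.

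| True rates | Shares attributed | Recorded | Rate ratio |
|---|---|---|---|
| 5% v 5% | 80% v 60% | 4% v 3% | 0.8/0.6 = 1.33 |
| 20% v 20% | 90% v 70% | 18% v 14% | 0.9/0.7 = 1.29 |
| 20% v 20% | 90% v 50% | 18% v 10% | 0.9/0.5 = 1.80 |
| 30% v 20% | 60% v 90% | 18% v 18% | 1.00 (true 1.50) |

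The first three rows create a difference. The last hides one.

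**4. How large is that in events?** First row: 172 × 0.05 = 8.6 true events per arm; 8.6 × 0.8 = 6.9 and 8.6 × 0.6 = 5.2 recorded, a gap of 1.7 events. The standard error of the log rate ratio is √(1/6.88 + 1/5.16 − 2/172) = 0.572. The 95% interval is exp(0.288 ± 1.96 × 0.572), about 0.43 to 4.1. Sampling noise is far larger than this illustrated bias.

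**5. Can the shares be estimated from the trial?** No. The denominator of each share includes the events that were not recorded.

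**The case against.** The related-only rule is a deliberate choice, applied consistently across Section 13, with a reason given: patients may have co-morbidities. This stands. The point is an improvement to a design choice, and a reader who inferred an error or an internal contradiction would go too far.

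A reader might also infer that all safety outcomes pass through the filter. They do not. Deaths, unplanned surgery on the affected knee and the ITT analysis of joint survival are outside it, and these are central to comparing KJD with KR.

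A reader might infer that the matter can never be checked. Section 17 allows source data verification with access to patient notes, Section 18 provides for consent to medical record access, and Section 12.2 schedules concomitant medications in both arms, which leaves an indirect trace. These are partial checks: verification is optional, sampled and not aimed at unreported events. The accurate statement is that attribution cannot be assessed from the complication data themselves.

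The illustrated bias rests on assumed figures and is small in events. The protocol names no between-arm test for complications and does not power secondary outcomes, so it gives no basis for quoting a false-positive risk. This also stands.

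Finally, recording every listed event would be heavy and could blur the comparison. The Section 13.2.2 list is expressly not exhaustive and includes leg pain, any infection needing antibiotics and a catch-all for cardio-pulmonary events. Background events common to both arms pull an all-event rate ratio towards 1. This is decisive against a broad remedy, and the fix is narrowed accordingly.

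**Conclusion.** The concern holds in limited form. For complications other than deaths and unplanned surgery on the affected knee, an unblinded local causality judgement decides whether an event exists in the data. If attribution differs between arms, recorded rates are biased by the ratio of the attribution shares, in either direction, and the trial data cannot reveal it.

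The documents do not show that attribution will differ, in which direction, or by how much. The figures above show the mechanism and are not estimates. The primary outcome, the sample size, re-operation and joint survival are not affected. This is a worthwhile, inexpensive improvement to a secondary safety comparison. It is best made before recruitment, because unrecorded events are hard to recover later.

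**What to change.** In Sections 13.2.2, 13.2.4 and 13.2.5, name a short closed set of discrete, verifiable events drawn from those already listed:

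- myocardial infarction
- angina
- pneumonia
- pulmonary embolism or other symptomatic venous thrombo-embolism
- stroke
- fracture in the affected or the non-affected limb
- osteomyelitis
- infection of the affected knee or leg, including pin sites

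Record every occurrence in both arms from randomisation to 24 months whatever the attribution, with relatedness as a field on the existing CRF. Report these events by arm twice: regardless of attribution, and restricted to those judged related. Adjust the Section 13.1 and 13.3 wording that unrelated events are not collected or reported, so that it excepts this set.

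Leave leg pain, infections elsewhere, the cardio-pulmonary catch-all and all other unrelated events under the current rule.

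Cost: a modest increase in site reporting, at visits that already collect complications and for events whose causality sites must already judge. The all-event comparison will include some background events that dilute a true difference, which is why the related-only comparison stays beside it.

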13.3. SAFETY REPORTING RESPONSIBILITIES

Principal Investigator (PI) (i.e. lead trial clinician at each recruiting research site or appropriate clinical individual identified in the APL)

1. Checking for complications during admission and follow-up, including using medical judgement in assigning:

- Causality, i.e. whether an untoward medical event is related (i.e. a complication which therefore needs to be reported) or unrelated (i.e. not a complication and therefore does not need to be reported)
- Seriousness
- Expectedness

3. To ensure all SCs and USCs up to 24 months are recorded and initially reported to the CTRU within 24 hours of the research site team becoming aware and to provide further follow-up information as soon as available.

4. To report SCs and USCs to the CTRU in-line with the protocol.

5. To report USCs to local committees in line with local arrangements.

Chief Investigator (CI) (or nominated individual in CI's absence)

1. Assign relatedness and expected nature of reported complications/untoward medical events where it has not been possible to obtain local assessment.

2. Undertake review of SCs and USCs. In the event of disagreement between local assessment and the CI, local assessment may be upgraded or downgraded by the CI prior to reporting to the main REC.

Clinical Trials Research Unit (CTRU)

1. Expedited reporting of USCs occurring within 24 months post-surgery to the REC and Sponsor according to HRA, CTRU SOPs and Sponsor timelines.

2. Preparing annual safety reports to the REC and periodic safety reports to TSC and DMEC as appropriate.

3. Notifying Investigators of SCs and USCs which compromise participant safety.

Trial Steering Committee (TSC)

In accordance with the Trial Terms of Reference for the TSC, periodically reviewing safety data and liaising with the DMEC regarding safety issues. See Section 21.2.2 for further detail about the responsibility of the TSC.

Data Monitoring & Ethics Committee (DMEC)

In accordance with the Trial Terms of Reference for the DMEC, periodically reviewing unblinded safety data to determine patterns and trends of events, or to identify safety issues, which would not be apparent on an individual case basis. See Section 21.2.3 for further detail about the responsibility of the DMEC.

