13.2.2. Expected complications – standard reporting

The following is a list of expected complications related to the administration of any research procedure including pre and post-operative complications associated with either surgical procedure or the use of general anesthetic and any further interventions on the affected knee (but are not limited to):

- Complex regional pain syndrome in the affected leg
- Anaesthesia reactions
- Stiffness in the affected leg needing manipulation under anaesthesia
- Pain in the affected leg
- Neuro-vascular injury in the affected leg

KARDS protocol v1.0_190927
- Compartment syndrome in the affected leg
- Infection needing topical, oral or systemic antibiotics
- Infection needing surgical intervention (details of surgical intervention to be provided on a separate form including the organism identified, treatment given, duration of symptoms and current status)
- Revision surgery in the affected leg
- Failure of external fixator frame or pins (breakage / cut out / loosening) (KJD arm only)
- Myocardial infarction
- Angina
- Pneumonia
- Pulmonary embolism
- Any other cardio-pulmonary event needing further treatment
- Cerebro-vascular accident (stroke)
- Fracture in non-affected limb

All expected complications will be reported from randomisation to end of follow-up on standard CRFs.

As the above complications, including those which fulfil the criteria of seriousness, are expected within the trial population they will not be subject to expedited reporting to the main REC. They will however, be included in the annual safety report provided to the main REC.

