13.2.3. All other complications – standard reporting

Information about the incidence and severity of all other complications (this includes all non-serious expected and non-serious unexpected complications) which occur from the date of randomisation to end of follow-up will be recorded on standard CRFs. These events will **not** be subject to expedited reporting requirements.

13.2.4.Serious Complications and Unexpected SeriousComplications – expedited reporting

The following (SCs) and USCs occurring within 24 months of surgery are subject to expedited reporting and must therefore be notified to CTRU **within 24 hours** of the clinical research staff becoming aware of the event:

- Symptomatic venous thrombo-embolism
- Osteomyelitis
- Fracture in affected limb
- Death within 6 weeks of surgery

Notifications must be sent to CTRU by fax or secure file transfer using the SC / USC CRF. Once all resulting queries have been resolved the CTRU will request the original form is posted to CTRU and a copy retained at site.

24 hr fax for reporting SC & USCs: [name] or

[contact]

For each SC and USC the following data will be collected:

- Start and end dates (if resolved)
- Full details of complication in medical terms with a diagnosis (if possible)
- Action / intervention
- Outcome
- An identifiable and authorised reporting source (i.e. the signature of the investigator or other medic authorised by the investigator at the reporting research site).

Any follow-up information on SCs and USCs must be faxed or sent by secure file transfer to the CTRU as soon as it is available. Events will be followed up until resolution or a final outcome has been reached. All USCs will be reviewed by the Chief Investigator (CI) and will be subject to expedited reporting to the Sponsor and the REC

by the CTRU on behalf of the CI in accordance with current HRA guidance, CTRU Standard Operating Procedures (SOPs) and Sponsor requirements.

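### Section 13.3 lets the unblinded Chief Investigator downgrade a site's assessment of a serious complication before the REC is told, so an event the site judged unexpected can leave expedited reporting

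*Protocol*

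**What the plan says.** Section 13.3 (Safety reporting responsibilities) has the site's Principal Investigator assign causality, seriousness and expectedness, and report serious complications (SCs) and unexpected serious complications (USCs) to the CTRU within 24 hours. The CI then reviews them. On disagreement, "local assessment may be upgraded or downgraded by the CI prior to reporting to the main REC".

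Section 13.2.4 says that all USCs are reviewed by the CI and "will be subject to expedited reporting to the Sponsor and the REC".

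Section 13.1 defines an unexpected complication as "the type of event that in the opinion of the investigator is not considered expected". It points to Section 13.2.2 for examples of expected complications and adds "note this is not an exhaustive list". The introduction to the list in Section 13.2.2 also leaves it open. Of the listed complications, serious ones included, that section says "they will not be subject to expedited reporting to the main REC". They are recorded on standard CRFs to the end of follow-up and go into the annual safety report to the REC.

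On relatedness, Section 13.1 says that "untoward medical events which are unrelated to the trial procedures are not being collected in this trial", and Section 13.2.5 repeats the rule.

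**The concern.** Expedited reporting exists so that an unforeseen serious harm reaches people outside the trial team quickly. Here the last step before the REC is a review by the CI. Section 20.1 makes the CI responsible for the design, management and reporting of the trial, and Section 7.1 describes the trial as not blinded to medical or trial staff. The CI may lower the site's assessment at that step. Section 13.3 asks for no reasons and does not require the site's view to be kept or to travel with the report.

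The expectedness test gives little to hold the judgement against. It rests on opinion plus a list of examples, so two assessors can classify the same serious event differently and both comply.

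Section 5.1 says that no KJD studies have been done in the UK in an NHS setting and that the evidence base is small. The harms most worth hearing about early are therefore those that nobody has listed.

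**Working it through.** No arithmetic applies. The check follows a serious complication that the site judged related, serious and unexpected through each change the CI could make.

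**Scope of the power.** In Section 13.3 the local assessment consists of causality, seriousness and expectedness. The sentence that allows an upgrade or downgrade names none of the three and excludes none. A separate item lets the CI assign relatedness and expected nature where no local assessment could be obtained, so at least those two are treated as within the CI's competence. The scope is unspecified rather than stated to be all three.

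**Timing.** The site's report reaches the CTRU within 24 hours on the site's own assessment. The CI's change is tied to the later report to the main REC.

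**Routes.**

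- *Unexpected to expected.* The event is no longer a USC. Under Section 13.2.2 it is not expedited to the REC. The expedited Sponsor report in Section 13.2.4 is also confined to USCs, so it lapses too. The event stays on a standard CRF and enters the annual REC report. An annual cycle means a delay of up to about 12 months for the individual event.
- *Serious to non-serious.* The event is no longer a USC and is not expedited (Section 13.2.3). It stays on a standard CRF.
- *Related to unrelated.* By the definition in Section 13.1 it is no longer a complication. Events judged unrelated at the outset are not collected. For an event already reported to the CTRU, the protocol does not say whether a later CI change recodes it, removes it or leaves it in place. Complications are a secondary outcome (Section 11.2), counted by event and by patient (Section 14.1), so the silence touches an analysis.

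**How open the list is.** Besides being non-exhaustive, Section 13.2.2 contains a residual category for cardio-pulmonary events that need treatment. It also lists pulmonary embolism for standard reporting, while Section 13.2.4 puts symptomatic venous thrombo-embolism among the events to be notified within 24 hours. The list is therefore not yet clear enough to constrain a reclassification.

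**What remains in place on each route.** The DMEC periodically reviews unblinded safety data (Section 13.3), by randomised group in closed session (Section 20.2.3). Sites report USCs to local committees under their own arrangements (Section 13.3). All deaths go on a separate CRF (Section 12.3.3), and additional knee surgery is recorded at every post-baseline visit (Section 12.2). Neither of these last two depends on a judgement of relatedness.

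**The case against.** The strongest case against runs as follows.

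- **Little is lost.** An event relabelled expected or non-serious remains on the CRFs, an expected event goes into the annual REC report, and the DMEC reviews unblinded safety data whatever the CI thinks. This stands. A reader might infer that an expected label takes events out of the trial data, or that one opinion can close the DMEC route. The documents support neither.
- **No passage deletes a downgraded event.** This stands too. A reader might infer that a change to unrelated removes the event from the complication outcome, but that goes beyond the text. The rule that does keep events out of the data is the site's own relatedness judgement, made before the CI sees anything. It is a separate matter, and limiting the CI's power would not change it.
- **There is no contradiction.** Section 13.2.4 itself places CI review ahead of the REC report and refers to HRA guidance, CTRU procedures and Sponsor requirements. Those documents are not shown and may require both assessments to be kept. This is fair, and the point is not put as a contradiction. It is that the protocol grants the power to downgrade without stating a limit, and cites nothing for that power in Section 13.3.
- **Closing the list and barring downgrades are policy choices.** True, but they are cheap, and the present wording leaves the alternative to individual opinion.

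What the objection does not meet is the core: the protocol expressly permits a downgrade before the REC is told, with no record of the site's view required.

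**Conclusion.** The point holds for expedited reporting. Sections 13.1, 13.2.2 and 13.3 together let an unblinded CI take a serious event that the site judged unexpected out of expedited reporting to the REC and Sponsor, without the site's view being kept or shown. If the event is moved to expected, the REC next sees it in the annual report. The point does not extend to loss from the CRFs through an expected or non-serious label, or to DMEC review. The effect of a CI change from related to unrelated on the complication outcome is unstated, which is a gap to close rather than a demonstrated loss.

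No frequency can be attached. The protocol gives neither a rate of unexpected serious complications nor a rate of disagreement between CI and site. The conclusion assumes that the CI, like other clinical and trial staff, knows the allocation, and that no unseen procedure already requires both assessments to be sent. It is a worthwhile and inexpensive improvement to participant safety, not a flaw that threatens the primary analysis.

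**What to change.** Amend the wording in three places.

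1. **Section 13.3, CI responsibilities.** Allow the CI to upgrade, but not to downgrade an event out of expedited reporting. Where the CI disagrees, report on the site's assessment, record the CI's view beside it, and send both to the REC and DMEC.
2. **Section 13.3 or Section 14.1.** State that an event already recorded as a complication stays in the complication analysis whatever the CI's later view of its causality.
3. **Sections 13.1 and 13.2.2.** For expedited reporting, treat any serious complication not on the Section 13.2.2 list as unexpected. The list can remain illustrative for other purposes. In the same edit, reconcile the pulmonary embolism entry with the venous thrombo-embolism entry in Section 13.2.4, and say whether the events named in Section 13.2.4 count as expected for REC purposes.

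The cost is a protocol amendment and a few more expedited reports, some of which the CI will regard as unnecessary. No design, sample size or data collection changes, beyond a place to record the CI's view.
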